15.4 Stratification Factors: N/A

15.5 Analysis of Secondary Endpoints

15.5.1 Secondary Objectives

Statistical analyses will be conducted for the following secondary objectives:

- The immunogenicity of NT-I7
- A preliminary assessment of the anti-tumor activity of NT-I7 in combination with atezolizumab, including the ORR, as measured by RECIST v1.1 and iRECIST, the DCR, DOR, PFS, and OS.

Descriptive statistics will be provided. Mean, standard deviation, median, minimum and maximum will be displayed for continuous variables, and numbers and percentages will be displayed for counts and binary variables. Kaplan-Meier estimates will be considered for time to event variables (DOR, PFS and OS). The analyses will be performed for each arm in Phase 2a, separately.

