Trial Type	Phase 1b/2a, non-randomized 2 arm, open label trial with initial NT-I7 dose escalation phase (phase 1b) followed by a dose expansion phase (phase 2a)
Primary Objective	To evaluate the safety and tolerability of NT-I7 in combination with atezolizumab (Phase 1b), including estimation of the maximum tolerated dose (MTD) and/or the recommended Phase 2 dose (RP2D) Phase 2a: To evaluate the Objective Response Rate (ORR) according to RECIST v1.1 and iRECIST, as determined by the investigator
Secondary Objectives	To evaluate immunogenicity of NT-I7 in combination with atezolizumab To make a preliminary assessment of the anti-tumor activity of NT-I7 in combination with atezolizumab
Exploratory Objectives	To make a preliminary assessment of PK parameters of NT-I7 in combination with atezolizumab To make a preliminary assessment of biomarkers that might act as pharmacodynamic indicators of activity of NT-I7 in combination with atezolizumab To make a preliminary assessment of biomarkers that might act as predictors of anti-tumor activity of NT-I7 in combination with atezolizumab
Dose Escalation Phase (Phase 1b)	NT-I7 will be escalated until a plateau of peripheral T-cell level and tumor infiltration of T-cells is reached or unacceptable toxicities.
End Points	Primary endpoint of safety and tolerability of NT-I7 in combination with atezolizumab and estimation of MTD or RP2D for the combination. Secondary endpoints of immunogenicity of NT-I7, Objective Response Rate (ORR), Disease Control Rate (DCR), Duration of Objective Response (DOR), Progression-Free Survival (PFS) and Overall Survival (OS).
Arm I (Phase 2a)	Anti-PD-1/PD-L1 naïve cSCC and MCC
Arm II (Phase 2a)	Anti-PD-1/PD-L1 relapsed/refractory MCC, cSCC and melanoma

Number of Trial Patients	Approximately 84 patients
Number of Clinical Sites	Approximately 8 clinical research sites are expected to participate in this study
Duration of Participation	Each patient will participate in the trial from the time the Informed Consent Form (ICF) is signed through final protocol-specified contact. The active study will end when the last patient completes the 90-day safety follow up visit, approximately 27 months after enrollment.
Estimated Duration of Trial	Trial is expected to be completed approximately 36 months after the last patient is enrolled.

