3. OBJECTIVES AND ENDPOINTS

This study will evaluate the safety and tolerability and assess the antitumor efficacy of NT-I7 in combination with atezolizumab (Phase 1b/2a) in patients with anti-PD-1/PD-L1 naïve or relapsed/refractory high-risk skin cancers (cSCC, MCC, melanoma). Specific objectives and corresponding endpoints for the study are outlined in Table 2.

Table 2 – Study Objectives and Endpoints

Objectives	Corresponding Endpoints
Primary Objective	

To evaluate the safety and tolerability of NT-I7 in combination with atezolizumab (Phase 1b), including estimation of the Maximum Tolerated Dose (MTD) and/or the Recommended Phase 2 Dose (RP2D)
 
Phase 2a: To evaluate the Objective Response Rate (ORR) according to RECIST v1.1 and iRECIST, as determined by the investigator
	
 - Incidence, nature, and severity of adverse events graded according to NCI CTCAE v5.0 - Incidence and nature of DLTs - Potential correlation with PK, pharmacodynamic, safety, and efficacy parameters - Objective Response Rate (ORR), defined as the percentage of patients who have at least one confirmed partial response (PR) or complete response (CR) according to RECIST v1.1 and iRECIST, as determined by the investigator
Secondary Objectives	

To evaluate immunogenicity of NT-I7 in combination with atezolizumab
 
To make a preliminary assessment of the anti-tumor activity of NT-I7 in combination with atezolizumab
	
 - Incidence of anti-drug antibody (ADA) to NT-I7 during the study relative to the prevalence of ADA at baseline - Disease Control Rate (DCR), defined as proportion of patients with a best overall response of CR, PR or stable disease (SD). - Duration of objective response (DOR), defined as the time from the first occurrence of a documented objective response to the time of the first documented disease progression or death from any cause, whichever occurs first, per RECIST v1.1 and iRECIST as determined by the investigator - Progression Free Survival (PFS), defined as the time from the first study treatment (Cycle 1, Day 1) to the first occurrence of progression or death from any cause, whichever occurs first, per RECIST v1.1 and iRECIST as determined by the investigator - Overall survival (OS), defined as the time from first study treatment (Cycle 1, Day 1) to death from any cause
Exploratory Objectives	

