1.2.1. Primary Study Objective

- To evaluate the safety and tolerability of NT-17 in combination with atezolizumab (Phase 1b), including estimation of the MTD and/or the RP2D
- To evaluate immunogenicity of NT-17
- To make a preliminary assessment of the anti-tumor activity of NT-17 in combination with atezolizumab

Sponsor:	NeolimmuneTech, Inc.		
Protocol:	NTT-106 (ION-02)		
Document Version No.:	1.0	Document Date:	20Nov2023

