5. CHANGES TO PLANNED ANALYSES

Due to the premature closure of the study the following changes are made in comparison to the protocol:

- AEs leading to withdrawal and DLTs will not be listed separately.
- Laboratory values will only be listed.
- irRC (iRECIST) will not be summarized.
- Efficacy summaries will be performed on Efficacy Population only.
- All phases will be summarized within the same table.
- Duration of Stable Disease will replace Duration of Response analysis, due to limited patient responses.

Sponsor:	NeolimmuneTech, Inc.		
Protocol:	NIT-106 (ION-02)		
Document Version No.:	1.0	Document Date:	20Nov2023

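### The protocol makes Phase 2a ORR both primary and secondary, and the SAP neither settles its status nor plans to show it by arm against the stated benchmarks

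*Protocol*

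**What the plan says.** Four places in the protocol give ORR a status.

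- Synopsis (1.1), Primary Objective row, and section 3, Table 2, both under the primary objective: "Phase 2a: To evaluate the Objective Response Rate (ORR) according to RECIST v1.1 and iRECIST, as determined by the investigator". The secondary endpoints in Table 2 are anti-drug antibodies, DCR, DOR, PFS and OS. ORR is not among them.
- Synopsis, End Points row: the primary endpoint is safety, tolerability and the MTD or RP2D. ORR comes in the next group: "Secondary endpoints of immunogenicity of NT-I7, Objective Response Rate (ORR), Disease Control Rate (DCR), Duration of Objective Response (DOR"), followed by PFS and OS. The row names no phase.
- Section 15.5.1, among the secondary objectives: "A preliminary assessment of the anti-tumor activity of NT-I7 in combination with atezolizumab, including the ORR, as measured by RECIST v1.1 and iRECIST". The method is "Descriptive statistics will be provided" and the scope is "The analyses will be performed for each arm in Phase 2a, separately".

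SAP 1.2.1, the primary study objective, opens with "To evaluate the safety and tolerability of NT-17 in combination with atezolizumab (Phase 1b), including estimation of the MTD and/or the RP2D". Efficacy appears only as "To make a preliminary assessment of the anti-tumor activity of NT-17 in combination with atezolizumab". The SAP numbering runs from 1.2.1 to 1.2.3, so a heading, and possibly other text, is missing from the copy reviewed. SAP 2.5.1 and 4.8.1 define ORR without calling it primary or secondary.

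Protocol 15.3 and SAP 4.1 give the same benchmarks: with 24 patients in Arm I, 17 or more responders give a 95% interval that excludes 45.25%; with 36 in Arm II, 6 or more exclude 5%. SAP 4.2.1 analyses efficacy in two pooled groups, the three lower doses of Phase 1b and the 1200 µg/kg dose from both phases. SAP 4.2.6 plans no subpopulation analyses. SAP section 5 lists six changes made because of premature closure, one being "Duration of Stable Disease will replace Duration of Response analysis, due to limited patient responses". None concerns the status of ORR.

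**The concern.** A phase 2a expansion sized around ORR in each arm should say whether ORR is the endpoint it is judged on. Here the answer depends on the page. Under Table 2, an arm whose interval includes its historical rate has missed the benchmark on the primary endpoint. Under 15.5.1, the same data are a descriptive secondary finding, and the End Points row lets the trial be summarised on safety and dose selection alone.

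The SAP was the last chance to settle this. It keeps the per-arm benchmarks in its sample-size section but plans efficacy summaries that merge both arms, and merge Phase 1b with Phase 2a at 1200 µg/kg. With no primary designation, nothing in it requires the report to set ORR by arm beside 45.25% and 5%.

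**Working it through.** **1. Is the conflict only a matter of phase?**

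| Place | Status of ORR | Phase covered |
|---|---|---|
| Protocol synopsis, Primary Objective row | Primary | Phase 2a |
| Protocol Table 2 | Primary | Phase 2a |
| Protocol synopsis, End Points row | Secondary | Not stated |
| Protocol 15.5.1 | Secondary, descriptive | Each arm of Phase 2a |
| Protocol 15.6.2 | No label | Not stated |
| SAP 1.2 as available | ORR not named | – |
| SAP 2.5.1 and 4.8.1 | No label | – |

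The End Points row could be read as Phase 1b only. Section 15.5.1 cannot, because it ties its analyses to the Phase 2a arms. Table 2 and 15.5.1 therefore conflict on the same phase and arms.

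**2. Reproducing the benchmarks.** Inputs from protocol 15.3: n = 24 with reference 45.25%, and n = 36 with reference 5%. The exact (Clopper-Pearson) two-sided 95% limits for x responders in n are

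lower = Beta quantile(0.025; x, n − x + 1); upper = Beta quantile(0.975; x + 1, n − x).

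| Result | ORR | Exact 95% CI | Excludes reference? |
|---|---|---|---|
| 16/24 | 66.7% | 44.7% to 84.4% | No (45.25%) |
| 17/24 | 70.8% | 48.9% to 87.4% | Yes |
| 5/36 | 13.9% | 4.7% to 29.5% | No (5%) |
| 6/36 | 16.7% | 6.4% to 32.8% | Yes |

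Both stated thresholds reproduce. Of the intervals tried (exact, Wilson, Wald, Agresti-Coull, Jeffreys, one-sided 95% exact), only the two-sided exact interval gives both 17 and 6.

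**3. Is error inflation part of the problem?** If the thresholds were used as a success rule, P(X ≥ 17 | 24, 0.4525) = 0.0102 and P(X ≥ 6 | 36, 0.05) = 0.0083. Over two independent arms, 1 − (1 − 0.0102)(1 − 0.0083) = 0.018. It is not; the fault is the missing designation.

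**4. How often would the label matter?** The documents give no target ORR, so the true rates below are assumptions, at full enrolment. The chance of falling short is 1 − P(X ≥ threshold).

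| Arm I true ORR | Below 17/24 | Arm II true ORR | Below 6/36 |
|---|---|---|---|
| 60% | 81% | 10% | 85% |
| 65% | 64% | 15% | 54% |
| 70% | 44% | 20% | 25% |
| 75% | 23% | 25% | 8% |
| 80% | 9% | – | – |

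The two descriptions diverge often for modest effects and seldom for large ones.

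**5. Arms that closed short.** SAP section 5 says the study closed prematurely. Take 20 patients as an illustration: 14/20 gives 45.7% to 88.1% and 4/20 gives 5.7% to 43.7%. The first excludes 45.25% and the second excludes 5%. A short arm has therefore not necessarily missed its benchmark.

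**The case against.** The best defence is that this is exploratory work with no confirmatory claim. The benchmarks only describe where an interval would fall. There is no alpha, power, target rate or go/no-go rule for Phase 2a, the objective is simply to evaluate ORR, and SAP 4.2.5 says no p-values will be reported. That stands. A reader might infer that an arm below 17/24 or 6/36 is a failed trial; the documents contain no rule by which it would fail.

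A reader might also infer that the protocol has no analysis for its primary efficacy endpoint. That goes too far: section 15.6.2 describes the principal response-rate analysis, counts progression, early death and unknown response as failures, and asks for 95% confidence intervals. It does not, however, say whether that analysis is primary or secondary.

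The most tempting inference is that the SAP authors knew the response counts and quietly demoted ORR. The text does not support it. It shows only that responses were known to be limited. The conflict was already in the protocol, the SAP lists ORR first among its efficacy variables and keeps both benchmarks, and a line naming ORR could have been lost with the missing 1.2.2 text. No change that would trigger the protocol's amendment clause in section 15 is shown.

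None of this removes the contradiction between Table 2 and 15.5.1, or the absence of a per-arm summary in the SAP.

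**Conclusion.** The point holds as a contradiction over endpoint status with a reporting consequence. Phase 2a ORR is primary in two places in the protocol and secondary in two, one of which expressly covers each Phase 2a arm. The SAP as available leaves this open and plans summaries that would not show ORR by arm against its own benchmarks. A result of 16/24 or 5/36 could be reported as missing the benchmark on the primary endpoint or as a descriptive secondary, and each description would have support in the text.

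The sample sizes, thresholds and interval arithmetic are sound and unaffected. The conclusion about the SAP assumes that no sentence naming ORR as primary was lost around 1.2.2. If one was, the protocol conflict and the pooling problem remain. How often the two descriptions would diverge rests on assumed true rates and full enrolment.

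**What to change.** - **SAP 1.2:** state that the Phase 2a primary endpoint is confirmed ORR by RECIST v1.1, investigator-assessed, separately in Arm I and Arm II. Protocol 11.1 already makes RECIST 1.1 the primary measure of response, and SAP section 5 drops the iRECIST summaries.
- **Protocol 15.5.1 and synopsis End Points row:** remove Phase 2a ORR from the secondary lists.
- **SAP 4.8.1:** alongside the dose-pooled summary, add Phase 2a ORR by arm with the exact two-sided 95% interval at the number of patients actually reached, compared with 45.25% and 5%. Wording in 1.2 alone would not produce this table.
- **Arms closed before 24 or 36 patients:** report the exact interval at the actual number and state that the planned size was not reached, rather than automatically calling the objective not met.
- **If ORR is meant to be secondary:** declare that in SAP section 5 as a change made after premature closure and after responses were known to be limited.

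The cost is a few lines of text and one extra table, with no new data. The downside for the sponsor is that an arm whose interval does not exclude its benchmark must be reported that way on the primary endpoint.

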15.5.2 Exploratory Endpoints

Statistical analyses will be conducted to determine the immune correlates of the clinical activity of the investigational treatment combination.

The endpoints will include the evaluation of the effect of the investigational treatment combination on the immune-bias of the TME, based upon baseline and post-baseline tumor biopsy comparisons of:

- Serum concentration of NT-I7 administered in combination with atezolizumab at specified timepoints for the following parameters: Area under the concentration time-curve (AUC), maximum serum concentration (C_{max}), minimum serum concentration (C_{min}), Clearance (CL)
- Number, distribution, and phenotype of tumor-infiltrating cells
- PD-L1 expression
- Expression of IFN γ and associated proinflammatory gene expression in the TME
- Changes in TME that correlate with response or provide information on potential actionable causes for lack of clinical benefit.

15.6 Reporting and Exclusions

15.6.1 Evaluation of Toxicity

All patients will be evaluable for toxicity from the time of their first treatment with atezolizumab and/or NT-I7 until 30 days after the last dose of study treatment.

15.6.2 *Evaluation of Response*

All patients enrolled in the study who received at least 1 cycle of study treatment will be assessed for response to treatment, even if there are major protocol treatment deviations or if they are ineligible. Each patient will be assigned one of the following categories: (1) CR, (2) PR, (3) SD, (4) PD, (5) early death from malignant disease, (6) early death from toxicity, (7) early death because of other cause, or (9) unknown (not assessable, insufficient data). [Note: By arbitrary convention, category 9 usually designates the “unknown” status of any type of data in a clinical database.]

All of the patients who met the eligibility criteria and received at least 1 dose of study treatment will be included in the main analysis of the response rate. Patients in response categories 4-9 should be considered to have a treatment failure (disease progression). Thus, an incorrect treatment schedule or drug administration does not result in exclusion from the analysis of the response rate. Precise definitions for categories 4-9 will be protocol specific.

All conclusions should be based on patients who received at least 1 cycle of study treatment. Sub-analyses may then be performed on the basis of a subset of patients, excluding those for whom major protocol deviations have been identified (early death due to other reasons, early discontinuation of treatment, major protocol violations, *etc.*). However, these sub-analyses may not serve as the basis for drawing conclusions concerning treatment efficacy, and the reasons for excluding patients from the analysis should be clearly reported. The 95% confidence intervals should also be provided.

APPENDIX A PERFORMANCE STATUS CRITERIA

ECOG Performance Status Scale		Karnofsky Performance Scale	
Grade	Descriptions	Percent	Description
0	Normal activity. Fully active, able to carry on all pre-disease performance without restriction.	100	Normal, no complaints, no evidence of disease.
		90	Able to carry on normal activity; minor signs or symptoms of disease.
1	Symptoms, but ambulatory. Restricted in physically strenuous activity, but ambulatory and able to carry out work of a light or sedentary nature (e.g., light housework, office work).	80	Normal activity with effort; some signs or symptoms of disease.
		70	Cares for self, unable to carry on normal activity or to do active work.
2	In bed <50% of the time. Ambulatory and capable of all self-care, but unable to carry out any work activities. Up and about more than 50% of waking hours.	60	Requires occasional assistance but is able to care for most of his/her needs.
		50	Requires considerable assistance and frequent medical care.
3	In bed >50% of the time. Capable of only limited self-care, confined to bed or chair more than 50% of waking hours.	40	Disabled, requires special care and assistance.
		30	Severely disabled, hospitalization indicated. Death not imminent.
4	100% bedridden. Completely disabled. Cannot carry on any self-care. Totally confined to bed or chair.	20	Very sick, hospitalization indicated. Death not imminent.
		10	Moribund, fatal processes progressing rapidly.
5	Dead.	0	Dead.

APPENDIX B REGULATORY, ETHICAL, AND STUDY OVERSIGHT CONSIDERATIONS

Regulatory and Ethical Considerations

- This study will be conducted in accordance with the protocol and with the following:
 - Consensus ethical principles derived from international guidelines including the Declaration of Helsinki and Council for International Organizations of Medical Sciences (CIOMS) International Ethical Guidelines.
 - Applicable ICH Good Clinical Practice (GCP) Guidelines.
 - Applicable laws and regulations.
- The protocol, protocol amendments, ICF, Investigator's Brochure, and other relevant documents (e.g., advertisements) must be submitted to an IRB/IEC by the Investigator and reviewed and approved by the IRB/IEC before the study is initiated.
- Any amendments to the protocol will require IRB/IEC and regulatory authority approval, when applicable, before implementation of changes made to the study design, except for changes necessary to eliminate an immediate hazard to subjects.
- The Investigator will be responsible for the following:
 - Providing written summaries of the status of the study to the IRB/IEC annually or more frequently in accordance with the requirements, policies, and procedures established by the IRB/IEC.
 - Notifying the IRB/IEC of SAEs or other significant safety findings as required by IRB/IEC procedures.
 - Providing oversight of the conduct of the study at the study center and adherence to requirements of 21 Code of Federal Regulations (CFR), ICH guidelines, the IRB/IEC, European regulation 536/2014 for clinical studies (if applicable), and all other applicable local regulations.
- After reading the protocol, each Investigator will sign the protocol signature page and send a copy of the signed page to IQVIA by e-mail to a contact [REDACTED] ([Appendix D](#)). The study will not start at any study center at which the Investigator has not signed the protocol.

Adequate Resources

The Investigator is responsible for supervising any individual or party to whom the Investigator delegates study-related duties and functions conducted at the study center.

If the Investigator/institution retains the services of any individual or party to perform study related duties and functions, the Investigator/institution should ensure this individual or party is qualified to perform those study-related duties and functions and should implement procedures to ensure the integrity of the study-related duties and functions performed and any data generated.

Financial Disclosure

Investigators and sub-Investigators will provide the Sponsor, via submission to IQVIA, with sufficient, accurate financial information as requested to allow the Sponsor to submit complete and accurate financial certification or disclosure statements to the appropriate regulatory authorities. Investigators are responsible for providing information on financial interests during the course of the study and for 1 year after completion of the study.

Informed Consent Process

- The Investigator or his/her representative will explain the nature of the study to the subject and answer all questions regarding the study.
- Subjects must be informed that their participation is voluntary. Subjects will be required to sign a statement of informed consent that meets the requirements of 21 CFR 50, local regulations, ICH guidelines, Health Insurance Portability and Accountability Act (HIPAA) requirements, where applicable, and the IRB/IEC or study center.
- The medical record must include a statement that written informed consent was obtained before the subject was entered in the study and the date the written consent was obtained. The authorized person obtaining the informed consent must also sign the ICF.
- Subjects must be re-consented to the most current version of the ICF(s) during their participation in the study.
- A copy of the ICF(s) must be provided to the subject.

Data Protection

- Subjects will be assigned a unique identifier. Any subject records or datasets that are transferred to the Sponsor will contain the identifier only; subject names or any information which would make the subject identifiable will not be transferred.
- The subject must be informed that his/her personal study-related data will be used by the Sponsor in accordance with local data protection law. The level of disclosure must also be explained to the subject.
- The subject must be informed that his/her medical records may be examined by Clinical Quality Assurance auditors or other authorized personnel appointed by the Sponsor, by appropriate IRB/IEC members, and by inspectors from regulatory authorities.
- The ICF will incorporate (or, in some cases, be accompanied by a separate document incorporating) wording that complies with relevant data protection and privacy legislation.
- The Sponsor or its representative will not provide individual genotype results to subjects, any insurance company, any employer, their family members, general physician, or any other third party, unless required to do so by law.
- Extra precautions are taken to preserve confidentiality and prevent genetic data being linked to the identity of the subject. In exceptional circumstances, however, certain individuals might see both the genetic data and the personal identifiers of a subject. For example, in the case of a medical emergency, the ION Coordinating Center, Sponsor or representative physician or an Investigator might know a subject's identity and have access to his or her genetic data. Also, regulatory authorities may require access to the

relevant files.

Administrative Structure

The Data and Safety Monitoring committee will include, at a minimum, NeoImmuneTech's Chief Medical Officer or designee, the Protocol PI, clinical site PIs and the ION Coordinating Center. The Principal Investigator and NeoImmuneTech, when appropriate, will invite other specialist individuals to participate in the review, e.g., PK scientists, statisticians, clinical specialists etc.

Table 6 – Study Administrative Structure

Function	Responsible Organization
Study Operations Management	ION Coordinating Center
Medical Monitoring	ION Coordinating Center and Protocol PI
On-site clinical monitoring	CRO – Avance Clinical, LLC
Study Master File	CRO – IQVIA
Data Management	CRO – Cytel, Inc.
Clinical Supply Management	Drug Information System integrated to eDC system
Biostatistics	CRO – Cytel, Inc.
Medical Writing	ION Coordinating Center and CRO - IQVIA
Data and Safety Monitoring Committee	Protocol PI, clinical site PIs, ION Coordinating Center and NIT's Chief Medical Officer or designee

Dissemination of Clinical Study Data

The results of the study should be reported within 1 year from the end of the clinical study. Irrespective of the outcome, the Sponsor, NeoImmuneTech, will submit to the Food and Drug Administration a summary of the results of the clinical study within 1 year from the end of the clinical study. It shall be accompanied by a summary written in a manner that is understandable to laypersons.

Data Quality Assurance

- All subject data relating to the study will be transmitted electronically. The Investigator is responsible for verifying that data entries are accurate and correct by electronically signing the eCRF.
- The Investigator must maintain accurate documentation (source data) that supports the information entered in the CRF.
- The Investigator must permit study-related monitoring, audits, IRB/IEC review, and regulatory agency inspections and provide direct access to source data documents.
- The ION Coordinating Center or designee is responsible for the data management of this study including quality checking of the data.
- Study monitors will perform ongoing source data verification to confirm that data entered into the CRF by authorized study center personnel are accurate, complete, and verifiable from source documents; that the safety and rights of subjects are being protected; and that the

study is being conducted in accordance with the currently approved protocol and any other study agreements, ICH GCP, and all applicable regulatory requirements.

- Records and documents, including signed ICFs, pertaining to the conduct of this study must be retained by the Investigator for 2 years following the date a marketing application is approved for the drug for the indication for which it is being investigated; or, if no application is to be filed or if the application is not approved for such indication, until 2 years after the investigation is discontinued and FDA is notified. No records may be destroyed during the retention period without the written approval of the Sponsor. No records may be transferred to another location or party without written notification to the Sponsor.

Source Documents

The Investigator/institution should maintain adequate and accurate source documents and study records that include all pertinent observations on each of the study center's subjects. Source data should be attributable, legible, contemporaneous, original, accurate, and complete. Changes to source data should be traceable, should not obscure the original entry, and should be explained if necessary (e.g., via an audit trail).

- Source documents provide evidence for the existence of the subject and substantiate the integrity of the data collected. Source documents are filed at the Investigator's study center.
- Data entered in the eCRF that are transcribed from source documents must be consistent with the source documents or the discrepancies must be explained. The Investigator may need to request previous medical records or transfer records, depending on the study. Also, current medical records must be available.
- Definition of what constitutes source data can be found in the ION Study Procedures Manual.

Study and Study Center Closure

The ION Coordinating Center reserves the right to close the study center or terminate the study at any time for any reason at the sole discretion of the Sponsor. Study centers will be closed upon study completion. A study center is considered closed when all required documents and study supplies have been collected and a study center closure visit has been performed.

The Investigator may initiate study center closure at any time, provided there is reasonable cause and sufficient notice is given in advance of the intended termination.

Reasons for the early closure of a study center by the Sponsor, NeoImmuneTech or the ION Coordinating Center may include but are not limited to:

- Failure of the Investigator to comply with the protocol, the requirements of the IRB/IEC or local health authorities, the Sponsor's procedures, or GCP guidelines.
- Inadequate recruitment of subjects by the Investigator.
- Discontinuation of further study treatment development.

Publication Policy

The data generated by this study are confidential information of the Sponsor. The Sponsor will make the results of the study publicly available. The publication policy with respect to the Investigator and study center will be set forth in the Clinical Trial Agreement.

- The results of this study may be published or presented at scientific meetings. If this is foreseen, the Investigator agrees to submit all manuscripts or abstracts to the Sponsor, NeoImmuneTech, before submission. This allows NeoImmuneTech to protect proprietary information and to provide comments.
- The Sponsor will comply with the requirements for publication of study results. In accordance with standard editorial and ethical practice, NeoImmuneTech will generally support publication of multicenter studies only in their entirety and not as individual study center data. In this case, one of the ION Investigators will be designated, by mutual agreement, as the Coordinating Investigator.
- Authorship will be determined by mutual agreement and in line with International Committee of Medical Journal Editors authorship requirements.

